most common clinical side effects of ticagrelor were dyspnea (13.8%), headache (6.5%), cough (4.9%), dizziness (4.5%), nausea (4.3%), bradycardia (4.4%) principally. Infrequent events included intracranial hemorrhage (0.3%) and severe bradycardia requiring pacemaker insertion (0.9%). Patients considered to be at high risk of bradyarrhythmic events will be excluded. The most important adverse effect associated with the use of ticagrelor is bleeding. The risk of major spontaneous bleeding with ticagrelor is 2.8% [9]. However, such bleeding prevalence occurred in the setting of long-term (12 months) trials, while our study is limited only to approximately 1week of ticagrelor therapy, thus reducing the risk of bleeding complications. All clinical events described above, if they were to occur, as well as death, myocardial infarction, stroke, and urgent revascularization procedure with PCI or coronary artery bypass grafting will be recorded. Bleeding data will be collected using PLATO definitions [14]. Clinical events will be evaluated by a local committee, comprised of 2 faculty members (2 cardiologists), not directly involved in the research. In the event of a report of a serious adverse event (major bleeding – defined as lifethreatening: fatal, symptomatic intracranial hemorrhage, leading to a drop in hemoglobin of at least 5 g/dL, significant hypotension requiring intravenous inotropes, requiring surgical intervention, or requiring transfusion of 4 or more units of blood; non-life-threatening: substantially disabling, intraocular bleeding leading to vision loss, or requiring at least 2 units of blood; thrombocytopenia <50,000) the local committee will meet and antiplatelet treatment management will be managed according to physician recommendation.

Definition of Adverse Events

An adverse event is any unintended or undesirable experience that occurs during the course of the clinical investigation whether or not it is considered to be therapy related. This includes any newly occurring event or previous condition that has increased in severity or frequency since the initiation of study treatment. Adverse events will be followed until resolution while the patient remains on-study. Once the patient is removed from study, events thought to be related to the study therapy will be followed until resolution or until the patient starts a new treatment regimen.

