Serious Adverse Events (SAE): An adverse event occurring while on study and considered related (reasonable possibility that the study treatment caused the adverse experience) to the study treatment that results in any of the following outcomes:

- Death

- A life-threatening adverse experience.

- A persistent or significant disability, incapacity, or is a congenital anomaly, or birth defect.

- Requires inpatient hospitalization, or prolongation of existing hospitalization.

The definition of serious adverse event also includes 'important medical event'. Medical and scientific judgment should be exercised in deciding whether expedited reporting is appropriate in other situations, such as important medical events that may not be immediately life-threatening or result in death or hospitalization but may jeopardize the patient and/or may require medical or surgical intervention to prevent one of the other outcomes listed in the definition above. These should also usually be considered serious. Examples of such events are intensive treatment in an emergency room or at home for allergic bronchospasm; blood dyscrasias or convulsions that do not result in hospitalization; or development of drug dependency or drug abuse.

Possible benefits

The present investigation is aimed to evaluate the PD effects of switching from ticagrelor to clopidogrel. This study is not designed to evaluate differences in clinical benefit. However, differences in antiplatelet profiles may potentially prompt further investigation of the clinical implication of this difference by means of a larger scale clinical study.

Potential Financial Risks or Benefits

None

Conflict of Interest

[name] is a consultant for Astra Zeneca, the maker of ticagrelor.

References

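### The SAE definition makes seriousness depend on relatedness, so a non-bleeding death judged unrelated to study treatment would not be classed as serious

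*Combined protocol and SAP*

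**What the plan says.** The combined protocol and SAP deals with safety events in two adjoining sections.

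- **Definition of Adverse Events, general definition.** An adverse event is any untoward experience that "occurs during the course of the clinical investigation whether or not it is considered to be therapy related". Causality plays no part.
- **Same section, SAE definition.** An SAE is "An adverse event occurring while on study and considered related" (a parenthesis glosses this as a reasonable possibility of causation) "to the study treatment that results in any of the following outcomes". Four outcome lines follow: death; a life-threatening experience; disability, incapacity or birth defect; and "Requires inpatient hospitalization, or prolongation of existing hospitalization".
- **Same section, important medical events.** The definition is extended to important medical events. For these, "Medical and scientific judgment should be exercised in deciding whether expedited reporting is appropriate in other situations", with the example of "important medical events that may not be immediately life-threatening or result in death or hospitalization but may jeopardize the patient". Relatedness is not mentioned again.
- **Possible Discomforts and Risk.** Deaths, infarctions, strokes and urgent revascularisations are recorded, and two cardiologists outside the research evaluate clinical events; neither step depends on relatedness. A later sentence begins "In the event of a report of a serious adverse event (major bleeding". Its parenthesis lists life-threatening and other major bleeding and thrombocytopenia below 50,000, and it ends "the local committee will meet and antiplatelet treatment management will be managed according to physician recommendation".

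**The concern.** Seriousness describes what happened to the patient. Relatedness is an opinion about why it happened. The SAE definition combines them, so whether a death or a hospitalization is labelled serious turns on a causality judgement. That judgement is made with treatment known, because the study is open-label, and no section says who makes it.

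What is at stake is the completeness and meaning of any list of SAEs drawn from this trial. A list that followed the definition to the letter could leave out a death that the trial had recorded. A reader would also be unsure which events the term covers, because Possible Discomforts and Risk uses it for a different set. The wording on expedited reporting leaves judgement to situations other than those in the main list. That suggests the main list is what otherwise prompts such reporting, but this is an inference: the document sets out no reporting procedure.

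**Working it through.** No sample size, power or event-rate figure is involved, so the check is to apply the two sections to test cases.

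**Step 1: how the definition is built.** One lead-in governs the whole outcome list, and the relatedness condition sits in that lead-in. An event must therefore be both related and have a listed outcome. This holds for 4 of the 4 outcome lines.

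**Step 2: test cases.**

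| Event | Main SAE definition | Listed after the term in Possible Discomforts and Risk |
|---|---|---|
| Non-bleeding death, judged unrelated | Not met | No, unless platelets were also below 50,000 |
| Hospitalised infarction, judged unrelated | Not met | No |
| Fatal bleed, judged unrelated | Not met | Yes |
| Bleed needing 2 units of blood, judged unrelated | Not met | Yes |
| Hospitalization without major bleeding or thrombocytopenia, judged related | Met | No |

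Row 1 is the main finding. It has to be limited to non-bleeding deaths because row 3 shows that a fatal bleed is called serious in the other section whatever its cause. Rows 3 to 5 show that the two scopes differ in both directions.

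**Step 3: does the important-medical-event clause close the gap?** It repeats no relatedness condition, so it leaves room to class a non-fatal unrelated event as serious by judgement. Its wording, however, is for events that fall short of death or hospitalization. It does not naturally reach row 1.

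**Step 4: how much exposure is there?** Inputs: run-in of 7±2 days (Research design); last sample at 10±3 days (Blood sampling); up to 80 patients (Study endpoints and sample size calculation), allocated 1:1:1:1, so 20 per group.

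- Groups B and D: (5 to 9) + (7 to 13) = 12 to 22 days.
- Groups A and C: one further washout day, because the Table S1 footnote counts from study drug administration, so 13 to 23 days. Counted from randomization, as under Blood sampling, the extra day drops out.
- Total: 40 × 12 + 40 × 13 = 1,000 to 40 × 22 + 40 × 23 = 1,800 patient-days. Divided by 365.25, this is about 2.7 to 4.9 patient-years.

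The document gives no expected number of SAEs, so no count of misclassified events can be derived.

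**The case against.** The other side has five fair arguments.

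1. **The relatedness standard is low.** The gloss asks only for a reasonable possibility, not proof. This stands, and it narrows the gap to events where even that possibility is rejected. It does not close it.
2. **The two definitions do not contradict each other.** A reader might infer that the AE and SAE definitions conflict. They do not: a broad class and a narrower, related subset are logically consistent. The point is that the subset is a poor definition of seriousness.
3. **The bleeding list may only say which events convene the committee.** If so, a narrower scope is its purpose, and the related hospitalization in the last row of the table is no defect. The text does not say that this is its purpose, however, and the reading does not explain the two-unit bleed: an event named as an SAE in one section still fails the outcome list in the other.
4. **The important-medical-event example is illustrative.** Nothing bars an investigator from reporting an unrelated death by judgement. True, but the definition does not require it.
5. **The consequences are hypothetical.** The Statistical analysis plan names no safety analysis, no SAE listing is described, and the events of most interest are captured anyway. This stands and sets the severity.

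**Conclusion.** The point holds on the text with high confidence, and its severity is low. A non-bleeding death, or a hospitalised infarction, judged to have no reasonable possibility of being caused by study treatment does not meet the main SAE definition. The same term also has a different scope in the neighbouring section. With about 2.7 to 4.9 patient-years of follow-up, few events are likely. The conclusion assumes only that the definition is applied as written.

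Three stronger readings are not supported:

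- **That such deaths go unrecorded or unreviewed.** Recording and evaluation carry no relatedness condition. The gap is in classification, not in capture.
- **That the relatedness condition keeps events from the committee meeting.** The meeting sentence has its own list. Even a related non-bleeding death, without thrombocytopenia below 50,000, is not on it, so changing the SAE definition would leave that prompt as it is.
- **That group C has no treatment against which to judge relatedness,** because its clopidogrel is missing from Study Medications. That section reads as a list of supplies and does not define the reference for causality. The 75 mg maintenance dose is also off the list for groups A and B, so group C cannot be singled out on that ground.

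The primary comparison of PRU at 48 hours, the secondary pharmacodynamic endpoints and the sample size are unaffected.

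**What to change.** 1. In the SAE definition, delete the condition that the event be considered related, so that seriousness rests on outcome alone.
2. Record relatedness for each event in a separate field, keeping the reasonable-possibility standard, and state the role of the person who assesses it.
3. Reconcile the use of the term in Possible Discomforts and Risk with the SAE definition, so that it has one stated scope. If the bleeding and thrombocytopenia list is meant only to say when the committee meets, the text should say so.

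Which events convene the committee, and how antiplatelet treatment is then managed, remain for the sponsor; no change to either is proposed.

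The cost is a few lines of protocol wording, one form field and slightly more SAE reporting. The two-cardiologist committee already exists, and no endpoint, sample size or analysis changes.

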	Consent	Baseline Labs*	PD testing	Genetic Testing	Study drug^	Baseline PD	Randomi- zation	Study drug	2 hrs PD [†]	Baseline PD [†]	Study drug	2 hrs PD [†]	24 hrs PD [†]	48 hrs PD [†]	72 hrs PD [†]	10±3 days PD [†]
Group A	Х	Х	Х	Х	Х	Х	Х	X**		Х	X***	Х	Х	Х	Х	Х
Group B	Х	Х	Х	Х	Х	Х	Х	X***	Х				Х	Х	Х	Х
Group C	X	Х	Х	Х	Х	Х	Х	X**		Х		Х	Х	Х	Х	Х
Group D	X	Х	Х	X	Х	Х	Х	X^{++}	Х				X	Х	Х	Х

Table S1. Summary of protocol procedures

* Baseline labs obtained within the past 180 days will be considered valid for screening purposes. If baseline labs are not available, these will need to be obtained prior to considering a patient eligible for study entry and start the run-in phase (patients will have 90 days to enter the study).

^ Ticagrelor LD 180mg followed by 90mg BID MD for 7 ± 2 days

[†] After Study Drug administration.
[§] 12 hours after last ticagrelor 90-mg dose.
^{§§} 24 hours after last ticagrelor 90-mg dose.

Screening visit, V1, V2 and V4-V7 are common for all groups.

**At V2, group A and C will receive a 90-mg maintenance dose of ticagrelor.

*** Clopidogrel 600 LD

⁺⁺ Ticagrelor 90mg BID for 10+3days

V3 will be needed only for group A and group C.

Group A: clopidogrel 600mg LD 24 hours after last MD of ticagrelor, followed by 75mg daily MD;

Group B: clopidogrel 600mg LD 12 hours after last MD of ticagrelor, followed by 75mg daily MD;

Group C: clopidogrel 75mg daily MD 24 hours after last MD of ticagrelor;

Group D: continue ticagrelor MD 90mg twice daily.

PD: pharmacodynamic; V: visit.
